**NIH-FDA Phase 2 and 3 IND/IDE Clinical Trial Protocol Template**

6.1, 6.2	Changed fill weight target of placebo capsules to 300mg ± 10%	Following the preparation of several batches of placebo capsules to-date it has been observed that there is a relatively high rate of poor encapsulation (i.e. rejected capsules) of these capsules leading to waste of the microcrystalline cellulose material used to make them as well as the empty capsule supply on hand. Lowering fill weight helps improve the yield of successful placebo capsules made during the capping process thus warranting a protocol update. The microcrystalline cellulose material is inert and possesses no pharmaceutical activity thus lowering the fill weight of placebo capsules is immaterial to study outcome measures.
6.1	The zinc citrate per capsule amount was added to the elemental zinc amount description	This additional detail was requested by IDS staff.
6.2	Changed beyond-use date from 30 days to 180 days	Initial selection for the beyond-use date was based on guidance from the Missouri Board of Pharmacy, which recommended use of clinical judgement. As such, a very conservative (and arbitrary) short dating of 30 days was used. Due to slower than expected enrollment this has led to several batches of study product having to be wasted. IDS staff recommended using the United States Pharmacopeia (USP) 795 standards for non-sterile compounding instead of the Missouri Board guidance. USP states more definitely the beyond-use date for compounded solid dosage forms can be up to 180 days.
6.2	Removed language 'at the direction of the primary investigator'	This removal was requested by IDS staff as their standard operating procedures includes routine disposal of unused study drug without notifying the primary investigator.

**NIH-FDA Phase 2 and 3 IND/IDE Clinical Trial Protocol Template**

10.1	Updated structure of Independent Safety Monitor (ISM)	ISM personnel description updated to reflect current personnel; frequency of monitoring changed to percentages of enrollment target to accommodate the slower than anticipated enrollment.
-------------	--	---

## STATEMENT OF COMPLIANCE

This trial will be conducted in accordance with the International Conference on Harmonization Good Clinical Practice (ICH GCP), applicable United States (US) Code of Federal Regulations (CFR), and the University of Missouri School of Medicine Terms and Conditions of Award. The Principal Investigator will assure that no deviation from, or changes to the protocol will take place without prior agreement from the Investigational New Drug (IND) or Investigational Device Exemption (IDE) sponsor, funding agency and documented approval from the Institutional Review Board (IRB), except where necessary to eliminate an immediate hazard(s) to the trial participants. All personnel involved in the conduct of this study have completed Human Subjects Protection and ICH GCP Training.

The protocol, informed consent form(s), recruitment materials, and all participant materials will be submitted to the IRB for review and approval. Approval of both the protocol and the consent form must be obtained before any participant is enrolled. Any amendment to the protocol will require review and approval by the IRB before the changes are implemented to the study. All changes to the consent form will be IRB approved; a determination will be made regarding whether a new consent form needs to be obtained from participants who provided consent, using a previously approved consent form.

## 1 PROTOCOL SUMMARY

### 1.1 SYNOPSIS

Title:	Evaluation of zinc and green tea extract supplementation on reduction in symptom duration and severity associated with community respiratory viral infections: a randomized control trial (ZiPhenol Study)
Study Description:	Zinc and green tea supplementation have both been independently studied for supporting immune health during cold and flu-like illness in non-hospitalized patients with clinical trials demonstrating promising but inconsistent results. However, combination therapy may offer an improved effect as the antioxidant compound, epigallocatechin gallate (EGCG), found in green tea has been demonstrated in-vitro to increase intracellular concentrations of free zinc. Elevation of intracellular zinc is associated with inhibition of RNA-dependent RNA polymerase, which is the enzyme required for viral replication in the host cell. This study seeks to evaluate the effect of combination supplementation using established doses of zinc and green tea extract (EGCG) on symptom duration and severity from cold and flu-like illness, including COVID-19, in adult community patients enrolled in a randomized placebo-controlled trial.
Objectives:	
Primary Objective:
 
Determine the impact of combination supplementation against placebo on symptom duration and severity in non-hospitalized adult patients acutely infected with a respiratory viral illness
 
Secondary Objectives:

1. Compare adverse events of combination supplementation against placebo
2. Compare patient-reported morbidity events of days missed from work or school and hospitalization or physician office visit(s) for respiratory viral illness related complications associated with combination supplementation versus placebo

**Endpoints:**

Primary Endpoint:

Rate of recovery from cold and flu-like symptoms will be determined by quantifying the proportion of patients achieving a daily total symptom severity score of 0 or 1 using an established 12 symptom scoring system with a severity scale ranging from 0-absent to 3-very severe for each symptom (max of 36 points) through seven days of follow-up.

Secondary Endpoints:

1. Rates of patient-reported adverse events including nausea, vomiting, indigestion, worsening of shortness of breath or difficulty breathing, allergic reaction including skin rash, and need to seek medical care (e.g. hospitalization or physician visit) for a suspected study drug related adverse effect
2. Rates of patient-reported days missed from work or school and hospitalization or physician office visit(s) for respiratory viral illness related complications

**Study Population:**

100 patients aged 18 years and older seeking medical care at University of Missouri Health Care Emergency Department for cold and flu-like illness will be targeted for enrollment. Men and women of all ethnicities will be included.

**Phase:**

2

**Description of  
Sites/Facilities Enrolling  
Participants:**

University of Missouri Health Care (MUHC) is a Level 1 Trauma Academic Medical Center in central Missouri with over 600 staffed beds. The Emergency and Trauma Center experiences nearly 80,000 patient visits each year from a diverse population and has a dedicated research center that conducts a broad range of research initiatives. Currently, over 30 publications have been indexed by PubMed from the MUHC Emergency Medicine Department.

**Description of Study**

Enrolled patients will be randomized (1:1) to either placebo or

**Intervention:**

combination supplementation consisting of zinc 33mg, green tea extract 267mg, and ascorbic acid 67mg each per capsule. Study subjects will be instructed to take three (3) capsules of either placebo or combination supplementation two (2) hours following a meal twice daily for five days. Patients will be followed-up for a period of seven consecutive days following randomization.

[figure not shown]
**Study Duration:**

May 30, 2022 - June 1, 2023

**Participant Duration:**

8 days (including day of enrollment)

## 1.2 SCHEMA

### 1.3 SCHEDULE OF ACTIVITIES (SOA)

Procedures	Screening/Enrollment/ Baseline Visit 1, Day 1	Study Visit 2, Day 2	Study Visit 3, Day 3	Study Visit 4, Day 4	Study Visit 5, Day 5	Study Visit 6, Day 6	Study Visit 7, Day 7	Study Visit 8, Day 8
Informed consent	X							
Demographics ‡	X							
Medical history ‡	X							
Randomization	X							
Administer study intervention	X-----X							
Daily telephone visits for collection of study endpoints	X-----X							
Concomitant medication review	X-----X							
Physical exam (including height and weight) ‡	X							
Vital signs ‡	X							
Height ‡	X							
Weight ‡	X							
Hematology ‡	X							
Serum chemistry ‡ a	X							
EKG (as indicated) ‡	X							
Adverse event review and evaluation	X-----X							
Radiologic/Imaging assessment ‡	X							
Other assessments (e.g., immunology assays, pharmacokinetic) ‡	X							

‡ - Indicates procedures done as part of routine care and not specific to study methods

a – Basic metabolic panel or complete metabolic panel

## 2 INTRODUCTION

### 2.1 STUDY RATIONALE

RNA viruses are common causes of respiratory infections in humans with limited treatments available, especially non-prescription options. Zinc and green tea supplementation have both been independently studied for supporting immune health during cold and flu-like illness in non-hospitalized patients with clinical trials demonstrating promising but inconsistent results. However, combination therapy may offer an improved effect as the antioxidant compound, epigallocatechin gallate (EGCG), found in green tea has been demonstrated in-vitro to increase intracellular concentrations of free zinc. Elevation of intracellular zinc is associated with inhibition of RNA-dependent RNA polymerase, which is the enzyme required for viral replication in the host cell. This study aim seeks to evaluate the effect of combination supplementation using established doses of zinc and green tea extract (EGCG) on symptom duration and

severity from cold and flu-like illness, including COVID-19, in community patients enrolled in a randomized placebo-controlled trial.

## 2.2 BACKGROUND

[figure not shown]
RNA viruses (e.g. rhinovirus, influenza, coronavirus, etc.) are common causes of respiratory infections in humans contributing to significant morbidity. It is estimated that over 500 million non-influenza respiratory infections occur each year in the U.S costing \$40 billion annually due to absenteeism and healthcare related expenditures. This disease burden has significantly increased in recent months as COVID-19 continues to impact patients across the world with over 7 million U.S. cases at the time of this writing. Currently, no Food and Drug Administration (FDA) approved oral therapy exists for preventing or treating non-influenza respiratory viral infections including COVID-19 thus the urgent need for research in developing new therapeutic options.

The COVID-19 pandemic has galvanized the medical community to innovate treatment options in real-time with little historical drug therapy experience to guide decision-making. Early attempts to manage the disease included repurposing existing FDA approved drug therapy with conflicting results. Among these agents included the antimalarial drugs chloroquine and hydroxychloroquine, azithromycin, and the antiretroviral lopinavir/ritonavir (Kaletra®). In May 2020 the FDA issued an emergency use authorization (EUA) for the intravenous antiviral agent remdesivir for treatment of severe COVID-19. This EUA was expanded to include treatment in all hospitalized patients regardless of disease severity; however, most patients with COVID-19 and other non-influenza respiratory viral illnesses do not require hospital stay leaving them with limited treatment options. Recently the FDA authorized use of newer therapies for COVID-19 in non-hospitalized patients including nirmatrelvir-ritonavir and molnupiravir, however, these are recommended for those only at high risk of progressing to severe disease leaving many healthier patients without options for disease management. This gap in care provides impetus to explore alternative treatment strategies including novel use of over-the-counter (OTC) products and supplements.

[figure not shown]
Zinc is associated with antiviral activity and has been demonstrated to improve recovery time in non-hospitalized patients with an acute viral respiratory illness. This effect is thought to be dependent on the availability of free or ionized zinc (iZn) released from the dosage form, and it has been observed that viral replication is inhibited in-vitro following increases in *intracellular* free zinc. However, ionized zinc is poorly permeable through the cell membrane and a high degree of variability exists between currently available zinc supplements in terms of free zinc bioavailability. Inconsistent real-world results with current over-the-counter (OTC) zinc lozenge products and other dosage forms warrant further investigation into approaches to overcome some of these limitations of zinc supplementation.

Green tea extract (GTE) is a commonly found dietary supplement with a variety of purposes for improving human health including weight loss, anti-inflammatory, cancer prevention, and cardiovascular health. Recently, few published and unpublished data described here indicate the ability of the primary catechin compound found in GTE, epigallocatechin-3-gallate (EGCG), to act as an effective zinc

ionophore. This activity has been demonstrated in-vitro using human embryonic kidney cells (HEK293) and concentrations of EGCG (0.1 - 1.5  $\mu$ M) achievable with established doses for human consumption (figure 1, unpublished data), and appears to be dependent on the extracellular zinc concentration (figure 2, unpublished data).

**Figure 1** Epigallocatechin-3-gallate (EGCG) increases intracellular labile zinc (Zn) levels  
A. HEK293 cells pre-loaded with 1  $\mu$ M FluoZin-3 were incubated in assay buffer containing no added Zn (basal) or in buffer containing 20  $\mu$ M Zn with 0.0, 0.1, 0.5, 1.0 or 1.5  $\mu$ M EGCG. Arbitrary units (A.U.) of fluorescence were measured on a Perkin Elmer plate reader at times indicated. B. Statistical analysis of the 240 min time point where \*P < 0.05; \*\*P < 0.01 represent significance of EGCG treatments compared with buffer containing 20  $\mu$ M Zn only.

**Figure 2** Higher concentrations of EGCG required to increase intracellular Zn when basal Zn is lower

HEK293 cells pre-loaded with 1  $\mu$ M FluoZin-3 were incubated in assay buffer containing no added Zn (basal) or in buffer containing 10  $\mu$ M Zn with 0.0, 0.1, 0.5, 1.0, 1.5, or 5.0  $\mu$ M EGCG. Arbitrary units (A.U.) of fluorescence were measured on a Perkin Elmer plate reader at 240 minutes. Statistical analysis of the 240 min time point where \* $P < 0.05$ .

The ability of EGCG to increase intracellular zinc for up to four hours in cell culture may translate to an improved effect of zinc supplementation in-vivo within the clinical context of an acute viral respiratory illness. This concept has been popularized following the COVID-19 pandemic with treatment protocols including hydroxychloroquine/chloroquine and zinc sulfate demonstrating mixed results and has prompted the development of several ongoing clinical studies. Previous clinical investigations of EGCG for non-COVID-19 viral illness have been limited to prevention of cold and flu-like infections with promising results. However, combination with zinc supplementation was not evaluated nor were patients with active viral infection enrolled in these studies. Currently, only one active study could be identified on clinicaltrials.gov that seeks to investigate the effect of EGCG on COVID-19 illness. This study did not include concomitant zinc supplementation nor did it evaluate the effect of supplementation on an acute infection.

Ascorbic acid is a well-known supplement often promoted for immune health during the cold and flu season despite inconsistent clinical data supporting its use in this manner. However, in the context of the proposed study supplement, ascorbic acid is intended to be used to enhance EGCG bioavailability as previously described in the literature. A similar approach will be used to formulate the zinc and EGCG combination supplement as described within this study protocol.

## 2.3 RISK/BENEFIT ASSESSMENT

### 2.3.1 KNOWN POTENTIAL RISKS

Risk to study subjects is anticipated to be in accordance with those associated with using the study drug components individually. The most common side effect expected is nausea as a 12-month clinical trial evaluating EGCG against placebo using a dosing scheme similar to the current proposal found an incidence of 10.2% vs. 4.8%, respectively. Taking study drug two hours following a meal is expected to limit nausea, but residual risk cannot be eliminated altogether. Secondly, hepatotoxicity has been reported with EGCG supplementation, but risk is associated with treatment durations beyond 2-4 weeks and doses higher than 800 mg/day. Our protocol includes only five days of treatment at a dose of 800 mg/day thus liver injury is not an anticipated risk to patients. Furthermore, patients with a history of chronic liver disease will be excluded. Zinc supplementation at the proposed doses may also contribute to increased risk a nausea/vomiting. A case report of severe nausea and vomiting occurred in a 17-year-old male 30 minutes following an acute ingestion of 570mg elemental zinc; however, no other complications were observed. Clinical studies evaluating zinc lozenges for the treatment of cold and flu-like illness have reported increased incidence of gastrointestinal upset as compared to placebo. One such trial using a total daily elemental zinc dose up to 207mg observed a rate of nausea and stomach distress of 13.5% with zinc vs 10.7% that was associated with placebo. No studies of zinc lozenge therapy for cold and flu have reported any serious adverse effects, however, long-term use of zinc supplementation has been associated with copper and iron deficiency. Although the current protocol includes only five days of treatment patients with a history of copper or iron deficiency will be excluded.

### 2.3.2 KNOWN POTENTIAL BENEFITS

Potential benefits of this study include elucidation of a novel combination of common dietary supplements to improve immune health during an acute respiratory viral illness in non-hospitalized patients. Positive results would be supportive to bring such a combination product to market with the intent to be used during an active infection as opposed to prevention. Most OTC remedies and herbal supplements are marketed for immune health as a preventative strategy, but few options exist for patients that are acutely ill. Common cough and cold products available to patients during an active infection are designed to only reduce severity of symptoms as opposed to improving immune health with the goal of shortening the disease process. This gap in care is of significance as it is estimated that over 500 million non-influenza respiratory infections occur each year accounting for \$40 billion annually in direct and indirect costs stemming from absenteeism and health-care related expenditures.

### 2.3.3 ASSESSMENT OF POTENTIAL RISKS AND BENEFITS

The risk-benefit assessment of this study intervention is considered favorable given the unmet clinical need for alternative therapies to help reduce the disease burden of community respiratory viral infections, including COVID-19. The study drug components are each a well-known dietary supplement with established dosing ranges and side effect profiles and are already individually used to help prevent or reduce cold and flu-like symptoms. Combination supplementation has not been evaluated in the method being proposed, but the additive risk of nausea is expected. The administration of study drug

two hours after a meal is anticipated to lower gastrointestinal disturbance, and the short duration of therapy planned will limit any possible long-term adverse effects associated with the higher doses of zinc and EGCG being used.

### 3 OBJECTIVES AND ENDPOINTS

OBJECTIVES	ENDPOINTS	JUSTIFICATION FOR ENDPOINTS
Primary		
Determine the impact of combination supplementation against placebo on symptom duration and severity in non-hospitalized adult patients acutely infected with a respiratory viral illness, including COVID-19	Rate of recovery from cold and flu-like symptoms defined as achieving a daily total symptom severity score of 0 or 1 within 7 days using an established 12 symptom scoring system with a severity scale ranging from 0-absent to 3-very severe for each symptom (max of 36 points). The 12 symptom domains include: nasal drainage, nasal congestion, sneezing, scratchy throat, sore throat, cough, headache, hoarseness, muscle ache, shivering or feverish, tiredness and difficulty in concentration. Mean total symptom severity scores and time to recovery will be compared between groups. The follow-up period will be seven consecutive days following randomization.	The primary outcome is derived from established clinical trial methodology evaluating the effectiveness of zinc supplementation for cold and flu-like illness. We selected this measure to maintain consistency within the published literature and to best assess patient relevant outcomes.
Secondary		
1. Compare adverse events of combination supplementation against placebo 2. Compare patient-reported morbidity events of days missed from work or school and hospitalization or physician office visit(s) for respiratory viral illness related complications associated with combination supplementation versus placebo	1. Rates of patient-reported adverse events including nausea, vomiting, indigestion, worsening of shortness of breath or difficulty breathing, allergic reaction including skin rash, and need to seek medical care (e.g. hospitalization or physician visit) for a suspected study drug related adverse effect 2. Rates of patient-reported days missed from work or school and hospitalization or physician office	Relevant safety endpoints were selected from established clinical trials assessing zinc and EGCG supplementation individually. Morbidity events of missed days from work or school or need to seek medical care for worsening respiratory illness is relevant to assess the

OBJECTIVES	ENDPOINTS	JUSTIFICATION FOR ENDPOINTS
	visit(s) for respiratory viral illness related complications	difference in disease burden between supplementation and placebo.
Tertiary/Exploratory		
Determine the impact of combination supplementation against placebo on symptom duration and severity in the COVID-19 positive subgroup of enrolled patients	Rate of recovery from cold and flu-like symptoms defined as achieving a daily total symptom severity score of 0 or 1 within 7 days using an established 12 symptom scoring system with a severity scale ranging from 0-absent to 3-very severe for each symptom (max of 36 points). The 12 symptom domains include: nasal drainage, nasal congestion, sneezing, scratchy throat, sore throat, cough, headache, hoarseness, muscle ache, shivering or feverish, tiredness and difficulty in concentration. Mean total symptom severity scores and time to recovery will be compared between groups.	This exploratory outcome is of interest given the continuous efforts to improve the management of COVID-19 associated disease, and advance the medical knowledge on possible remedies to better improve outcomes in non-hospitalized patients. Positive findings would garner interest to design a randomized control study exclusivity enrolling COVID-19 patients

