## 9.2 SAMPLE SIZE DETERMINATION

The target number of subjects to be enrolled during the study period occurring May 2022 – June 2023 is 100 (50 patients randomized to placebo and 50 to the supplementation group). This target is derived from a similarly conducted study evaluating zinc supplementation (without green tea extract) in a comparable adult population as identified with the current proposal. Based on an assumption that 60% of patients taking study drug and 30% in the placebo group would recover from cold and flu-like symptoms after five days of treatment a total of 84 patients would be sufficient to reach 80% power with a two tailed p value <0.05 to detect differences between groups. The power calculation was

$$N_1 = \left\{ z_{1-\alpha/2} * \sqrt{\bar{p} * \bar{q} * (1 + \frac{1}{k})} + z_{1-\beta} * \sqrt{p_1 * q_1 + (\frac{p_2 * q_2}{k})} \right\}^2 / \Delta^2$$

$$q_1 = 1 - p_1$$

$$q_2 = 1 - p_2$$

$$\bar{p} = \frac{p_1 + kp_2}{1 + K}$$

$$\bar{q} = 1 - \bar{p}$$

$$N_1 = \left\{ 1.96 * \sqrt{0.45 * 0.55 * (1 + \frac{1}{1})} + 0.84 * \sqrt{0.3 * 0.7 + (\frac{0.6 * 0.4}{1})} \right\}^2 / 0.3^2$$

$$N_1 = 42$$

$$N_2 = K * N_1 = 42$$

$p_1, p_2$  = proportion (incidence) of groups #1 and #2  
 $\Delta = |p_2 - p_1|$  = absolute difference between two proportions  
 $n_1$  = sample size for group #1  
 $n_2$  = sample size for group #2  
 $\alpha$  = probability of type I error (usually 0.05)  
 $\beta$  = probability of type II error (usually 0.2)  
 $z$  = critical Z value for a given  $\alpha$  or  $\beta$   
 $K$  = ratio of sample size for group #2 to group #1

performed using an online tool located at <https://clincalc.com/stats/samplesize.aspx> with the following calculations performed:

The anticipated dropout rate is 5% based on a large randomized control study evaluating safety of EGCG following 12 months of treatment using a similar daily dosage as the current proposal. No interim analysis is planned; power calculation is for primary endpoint only.

The primary outcome will be compared using the Chi-square test. Secondary outcomes will be assessed using the Chi-square test for categorical data and student's t-test for continuous data. An exploratory analysis comparing the primary outcome among COVID-19 only patients will also be conducted. All inferential testing will be based on intention-to-treat.

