#### 9.4.2 ANALYSIS OF THE PRIMARY EFFICACY ENDPOINT(S)

The primary endpoint will be determined from observing the proportion of patients (expressed as percentage) recovered from cold and flu-like symptoms (defined as scoring 0 or 1 daily total symptom severity score) following seven days of follow-up. Recovery from cold and flu-like symptoms will be categorically assessed as a single endpoint. The difference in recovery rates between study drug and placebo will be compared using Chi-squared test and be expressed with 95% confidence intervals. Analysis will be performed based on intention-to-treat. Missing data will be handled by last observation carried forward based on most recent self-reported total daily symptom severity score.

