#### 9.4.9 EXPLORATORY ANALYSES

The impact of combination supplementation against placebo on symptom duration and severity in the COVID-19 positive subgroup of enrolled patients will be assessed as an exploratory endpoint. This outcome will be determined from observing the proportion of COVID-19 positive patients (expressed as percentage) recovered from cold and flu-like symptoms (defined as scoring 0 or 1 daily total symptom severity score) following seven days of follow-up. Recovery from cold and flu-like symptoms will be categorically assessed as a single endpoint. The difference in recovery rates between study drug and placebo will be compared using Chi-squared test and be expressed with 95% confidence intervals. Analysis will be performed based on intention-to-treat. Missing data will be handled by last observation carried forward based on most recent self-reported total daily symptom severity score.

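### Does promising a comparison of time to recovery without naming a time-to-event method leave the trial's conclusion open?

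*Combined protocol and SAP*

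**What the plan says.** Section 3 defines recovery in the primary row as "defined as achieving a daily total symptom severity score of 0 or 1 within 7 days", and the synopsis says the rate "will be determined by quantifying the proportion of patients achieving a daily total symptom severity score of 0 or 1" over the seven days of follow-up. The same Section 3 cell adds: "Mean total symptom severity scores and time to recovery will be compared between groups". The exploratory COVID-19 row repeats that sentence. The Section 9.1 hypothesis concerns both duration and severity.

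Section 9.4.2 takes as the primary endpoint the proportion "recovered from cold and flu-like symptoms (defined as scoring 0 or 1 daily total symptom severity score) following seven days of follow-up". It treats this as a single categorical endpoint, compares the arms by chi-square on all randomized patients, and adds: "Missing data will be handled by last observation carried forward based on most recent self-reported total daily symptom severity score". Section 9.4.9 handles duration and severity in the COVID-19 subgroup in the same way: "This outcome will be determined from observing the proportion of COVID-19 positive patients (expressed as percentage) recovered from cold and flu-like symptoms".

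Section 9.2 assigns chi-square to the primary outcome. For secondary outcomes it assigns chi-square or Student's "t-test for continuous data", and 9.4.3 applies the latter only to mean days missed. The sample size assumes that "60% of patients taking study drug and 30% in the placebo group would recover from cold and flu-like symptoms after five days of treatment".

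No Kaplan-Meier estimate, log-rank test, censoring rule or formal definition of time to recovery appears. Mean severity score, promised in the same Section 3 sentence, has no stated method either.

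**The concern.** A comparison listed beside the primary endpoint has no method. Follow-up stops at Day 8, so patients not recovered by then have no observed recovery time, and different ways of handling them give very different analyses. If that choice were made after unblinding, it could be steered by the result.

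The recovery rule also seems to be worded in two ways. Section 3 reads as ever reaching 0 or 1. The phrase in 9.4.2, combined with carrying the latest score forward, could mean status on the last day. The two differ for patients who recover and then worsen, and this would touch the one confirmatory test.

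Finally, 9.2 attaches its rates to five days of treatment while the endpoint runs to seven days, so the stated power might belong to another time point.

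**Working it through.** **1. The plan's own figure.** From 9.2: p1 = 0.30, p2 = 0.60, equal arms, two-sided 0.05, 80% power, pooled proportion 0.45.

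N per arm = {1.96 × √(0.45 × 0.55 × 2) + 0.84 × √(0.3 × 0.7 + 0.6 × 0.4)}² / 0.3² = (1.379 + 0.563)² / 0.09 = 41.92, rounded up to 42 per arm and 84 in total. This matches the plan. Exact binomial power of the uncorrected chi-square test is 82.8% at 42 per arm and 87.6% at 50; the normal approximation gives 80.0% and 86.6%. The sample size is correct.

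**2. How many patients lack a recovery time.** If 30% and 60% are seven-day rates: 50 × 0.70 + 50 × 0.40 = 35 + 20 = 55 of 100. If they are day-5 rates, more patients recover by Day 8. Four hypothetical sets of seven-day rates give:

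- 39%/72%: 30.5 + 14 = 44.5
- 39%/65%: 30.5 + 17.5 = 48
- 50%/83%: 25 + 8.5 = 33.5
- 50%/72%: 25 + 14 = 39

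So unrecovered patients are more than half of the trial only under the seven-day reading.

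**3. What different methods would give.** Simulation at 50 per arm with seven daily calls and three assumed curves ending at 30% and 60% (20,000 trials; 4,000 for the recovered-only t-test). Chi-square power is 87.6% in every row.

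| Assumed curves | Log-rank | t-test, unrecovered set one day after the last call | t-test, recovered only |
|---|---|---|---|
| Constant hazards | 87.5% | 82.5% | 8.5% |
| Weibull, shape 2 | 87.9% | 80.0% | 6.8% |
| Constant hazards, effect ends at day 5 | 90.1% | 92.6% | 31.2% |

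The low figures belong to a t-test restricted to recovered patients. The plan does not assign that test to this outcome, and it conditions on something that happens after randomization. The log-rank test, the usual choice, performs almost the same as the primary test.

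**4. A case where the log-rank test gains.** Assume placebo reaches 60% by Day 8 and the active arm follows the same curve two days earlier, capped at 70%. Chi-square power is 18% and log-rank 49%. In the same example the t-test with a value assigned to the unrecovered reaches 77%, and the recovered-only t-test about 90%. The ranking of methods therefore depends on the assumed curve, and the example does not show that the plan needs the log-rank test in particular.

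**5. The recovery rule, side by side.**

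- The synopsis and Section 3 speak of achieving the score through, or within, seven days: an ever-reached rule.
- The form in 8.1 records recovery yes or no for each of Days 2 to 8, which fits that rule.
- Section 9.4.3 uses the same seven-day phrase as 9.4.2 for adverse events, missed days and medical visits. These count if they happen at all during follow-up. It applies a matching carry-forward rule to them.

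So neither the phrase nor the carry-forward rule signals end status. Under an ever-reached rule, carrying a score forward neither creates nor removes a recovery: a score of 0 or 1 has already counted, and a higher score leaves the patient not recovered.

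If end status were used and 10% or 20% of recovered patients in both arms relapsed (an assumption), the rates would be 0.54 against 0.27, or 0.48 against 0.24. Exact power at 50 per arm would be 80.3% or 71.5%.

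**6. The five-day wording.** Section 9.1 uses a similar five-day phrase to describe the regimen and in the next sentence places the analysis after seven days of follow-up. Section 9.2 says the power calculation is for the primary endpoint. Taken together, 30% and 60% are most naturally the rates for the seven-day endpoint. A day-5 reading is possible but not shown.

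**The case for a change.** The strongest opposing case is that Section 3 lists time to recovery in addition to the recovery rate, so the proportion cannot stand in for it. The spread in the table, from 7% to 93%, shows how much an analyst could gain or lose by choosing late. Naming a method would need no extra patients or data. There is also a real trap: patients hospitalized before recovery leave follow-up (7.1). If an assumed 10% of an arm were removed and censored at their last call, Kaplan-Meier recovery at Day 8 would read 64% instead of 60%, or 32% instead of 30%.

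It stands that the method is unstated, for time to recovery and for mean severity score alike, and that writing it down would be tidy. It does not stand that the plan as written gives a wrong answer. The wide spread comes from including a recovered-only t-test that the plan does not call for. The censoring bias belongs to one careless way of running a method the plan does not contain; under the plan's own rule a removed patient keeps the last score, so one removed before recovery counts as not recovered. The efficacy conclusion rests on the chi-square test, whose population, significance level, endpoint and missing-data rule are all fixed.

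**Conclusion.** No change is needed. This is missing detail about supporting comparisons, of the kind a trial statistician fills in a standard way: time to the first score of 0 or 1 over Days 2 to 8, with patients removed before recovery kept as not recovered. Daily recovery status is already collected. At the design rates that analysis has 88% to 90% simulated power against 87.6% for the primary test, so its absence costs little. Any result from it is supporting evidence only.

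The two wordings of the recovery rule resolve to ever reaching 0 or 1 by Day 8 once 9.4.2 is read with the synopsis, Section 3, 8.1 and 9.4.3. The five-day phrase in 9.2 is loose wording around a correct calculation.

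The power figures take 30% and 60% as seven-day rates. The recovery curves and the convergence, relapse, censoring and day-5 inputs are assumptions that the documents do not supply, and they show no defect in the stated plan.
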